9.1.15.3 Collection of CSF for PK Sampling

It is planned that CSF samples (1.25 mL per sample) for determination of TAK-071 will be collected predose (within 30 minutes before dosing) and at 0.5, 2, 4, 6, and 12 hours postdose in Cohort 3 and predose (within 30 minutes before dosing) and at 4, 8, 12, 24, and 36 hours post last dose in Cohort 9.

The procedure will be performed by an experienced anesthetist using local anesthetic (used to numb the skin and tissues) injected into the skin and disc space between the lumbar vertebrae to prevent discomfort during the procedure. An indwelling spinal catheter will be inserted into the subarachnoid space at the level of the L2 to L3 or L3 to L4 intervertebral space by trained personnel at the site. The procedure will be performed under sterile conditions, and the subject will be closely observed and monitored during the CSF collection.

Instructions for CSF collection and lumbar x-ray are provided in the Study Manual.

If measured concentrations in Cohort 3 are excessively low, ie, most time points are below the limit of quantification of the assay, TAK-071 CSF concentrations may also be determined in subsequent SRD cohorts until a dose deemed to provide adequate brain penetration is identified (eg, a dose that provides CSF concentrations analogous to the efficacious free [estimated] plasma concentrations observed in preclinical animal models). A different criterion might be applied.

CSF sampling time points may be adjusted based on the preliminary emerging PK data; the total number of CSF samples collected per subject will not exceed the planned number.

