10.1.3 Additional Points to Consider for PTEs and AEs

An untoward finding generally may:

- Indicate a new diagnosis or unexpected worsening of a pre-existing condition. (Intermittent events for pre-existing conditions underlying disease should not be considered PTEs or AEs.)
- Necessitate therapeutic intervention.
- Require an invasive diagnostic procedure.
- Require discontinuation or a change in dose of study drug or a concomitant medication.
- Be considered unfavorable by the investigator for any reason.
- PTEs/AEs caused by a study procedure (eg, a bruise after blood draw) should be recorded as a PTE/AE.

Diagnoses vs signs and symptoms:

- Each event should be recorded to represent a single diagnosis. Accompanying signs (including abnormal laboratory values or ECG findings) or symptoms should NOT be recorded as additional AEs. If a diagnosis is unknown, sign(s) or symptom(s) should be recorded appropriately as a PTE(s) or as an AE(s).

Laboratory values and ECG findings:

- Changes in laboratory values or ECG parameters are only considered to be PTEs or AEs if they are judged to be clinically significant (ie, if some action or intervention is required or if the investigator judges the change to be beyond the range of normal physiologic fluctuation). A laboratory re-test and/or continued monitoring of an abnormal value are not considered an

intervention. In addition, repeated or additional noninvasive testing for verification, evaluation or monitoring of an abnormality is not considered an intervention.

- If abnormal laboratory values or ECG findings are the result of pathology for which there is an overall diagnosis (eg, increased creatinine in renal failure), the diagnosis only should be reported appropriately as a PTE or as an AE.

Pre-existing conditions:

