10.2.1.2 PTE and AE Reporting

At each study visit, the investigator will assess whether any subjective AEs have occurred. A neutral question, such as “How have you been feeling since your last visit?” may be asked. Subjects may report AEs occurring at any other time during the study. Subjects experiencing a serious PTE must be monitored until the symptoms subside and any clinically relevant changes in laboratory values have returned to Baseline or there is a satisfactory explanation for the change. Nonserious PTEs, related or unrelated to the study procedure, need not to be followed-up for the purposes of the protocol.

All subjects experiencing AEs, whether considered associated with the use of the study drug or not, must be monitored until the symptoms subside and any clinically relevant changes in laboratory values have returned to Baseline or until there is a satisfactory explanation for the changes observed. All PTEs and AEs will be documented in the PTE/AE page of the eCRF, whether or not the investigator concludes that the event is related to the drug treatment. The following information will be documented for each event:

1. Event term.
2. Start and stop date and time.
3. Frequency.
4. Severity.

5. Investigator's opinion of the causal relationship between the event and administration of study drug(s) (related or not related) (not completed for PTEs).
6. Investigator's opinion of the causal relationship to study procedure(s), including the details of the suspected procedure.
7. Action concerning study drug (not applicable for PTEs).
8. Outcome of event.
9. Seriousness.

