The safety and tolerability of donepezil alone will be evaluated during the donepezil dosing phase (before TAK-071 is given in Cohorts 10 to 12) during the 3-week pretreatment period, and the safety and tolerability of donepezil in combination with TAK-071 (Cohorts 20 to 22) will be evaluated by assessing AEs, clinical laboratory results, physical examination findings, ECG findings, bowel function, and vital signs.

In addition to safety monitoring, TAK-071 plasma and urine PK profiles will be generated and PK parameters derived. It is planned that CSF samples for PK analysis will be obtained in Cohort 3 (following a single dose) and Cohort 9 (at steady-state). Pharmacodynamic (PD)

Approximately 186 subjects are expected to be randomized in this study.

End of study is defined as the date of last visit of the last subject for last clinical assessment.

The treatment groups and cohorts are outlined in Table 4.a.

Table 4.a Overview of Treatment Cohorts

Group	Cohort	Age (years)	Type	Regimen	Number of Subjects per Cohort		Total
					TAK-071	Placebo	
SRD (a)	1 to 6, 18, and 19	18-55	HV	Single	6	2	64
SRD + donepezil post TAK-071 treatment (a, b)	20 to 22	18-55	HV	Single	6	3 (+3 donepezil)	36
MRD (a)	7, 8	18-55	HV	1 dose QD for 21 days	6	2	16
MRD (a)	9	18-55	HV	1 single dose, 7-day washout, 1 dose QD for 21 days	6	2	8
MRD + donepezil pretreatment (a, c)	10 to 12	18-55	HV	1 dose QD for 21 days	6	2	24
MRD	13 to 15	20-55	jHV	1 single dose, 7-day washout, 1 dose QD for 21 days	5	1	18
Subjects with MCI or mild AD (a)	16	55-90	MCI or mild AD (d)	21 days TAK-071 QD (Treatment A) or 21 days of matching placebo (Treatment B). Subjects will be randomized to 2 sequences (AB or BA), with 21 days washout between treatment sequences.	NA	NA	up to 8 (minimum of 6)
Relative BA and FE (e)	17	18-55	HV	Single dose in each of 3 periods with washout period of 21 days after Periods 1 and 2	12	NA	12
						Total:	186

jHV=Japanese healthy volunteers, FE=food effect, HV=healthy volunteers, NA=not applicable.

(a) Non-Japanese subjects.

(b) Donepezil (10 mg) will be given as a single dose as an over-encapsulated oral tablet, 24 hours post TAK-071 dose.

[figure not shown]
(c) Donepezil (5 mg QD) will be given as an oral tablet daily for 3 weeks prior to dosing and during the TAK-071 dosing interval.

(d) Subjects with MCI or mild AD (non-Japanese) who have been stable on 10 mg donepezil treatment for at least 21 days or who consent to donepezil run-in period.

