5.0 ANALYSIS ENDPOINTS

5.1 Primary Endpoints

The following safety parameters will be analyzed as primary endpoints:

- Percentage of subjects who have at least 1 treatment-emergent adverse event (TEAE).
- Percentage of subjects who meet the Takeda markedly abnormal value (MAV) criteria at least once postdose for the following:
 - Clinical laboratory parameters.
 - Vital sign measurements.
 - ECG parameters.

PK parameters of TAK-071 in plasma following a single dose (Day 1) and at steady-state (after the final dose following multiple dosing) will be analyzed as primary endpoints:

- t_{\max} .
- C_{\max} in plasma.
- Area under the plasma concentration-time curve from time 0 to 24 hours (AUC_{24}).
- Area under the plasma concentration-time curve from time 0 to infinity, calculated using the observed value of the last quantifiable concentration (AUC_{∞}) (single dose only [Day 1]).

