7.12 Safety Analysis

Within each part (SRD cohorts, MRD cohorts, Cohort 16, and Cohort 17), for the non-Japanese and Japanese SRD and MRD cohorts separately, all safety summary tables will be presented by the pooled placebo group, each TAK-071 dose level, TAK-071 overall, and overall total within each part (SRD cohorts, non-Japanese MRD cohorts, Japanese MRD cohorts, Cohort 16, and Cohort 17) in the Safety Set. Safety data collected after administration of study drug under fed conditions will be summarized separately from data collected during administration of the same dose level under fasted conditions.

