7.12.1 Adverse Events

A PTE will be defined as any untoward medical occurrence in a clinical investigation subject who has signed informed consent to participate in a study but prior to study drug (TAK-071 or placebo) administration or increase in dose/start of donepezil prior to TAK-071 dose. A TEAE will be defined as an AE or a serious AE (SAE) that occurs or gets worse after receiving the first dose of study drug and within 30 days (onset date – last date of dose + 1 ≤ 30) after the last dose of study drug. A TEAE may also be a pretreatment AE or a concurrent medical condition diagnosed prior to the date of first dose of study drug that increases in severity after the start of dosing. AE data with onset occurring more than 30 days after last dose of study drug (AE start date – last dose date > 30) will be listed, but not included in the summary tables.

AE verbatim reported terms will be coded by system organ class, high-level term and preferred term using MedDRA, version to be delineated in the CSR.

TEAE summary tables will include numbers and percentages of subjects experiencing at least one AE by system organ class (SOC) and preferred term (PT) and will be tabulated for SRD

cohorts, non-Japanese MRD cohorts, Japanese MRD cohorts, Cohort 16, and Cohort 17. TEAEs will be summarized according to the treatment most recently received prior to the onset of the event. The TEAE summaries for SRD cohorts, non-Japanese MRD cohorts, Japanese MRD cohorts will also include a treatment group for TAK-071 overall, including all TEAEs summarized for any dose level of TAK-071.

The following is a list of AE summary tables to be generated:

- Overview of TEAEs.
- TEAEs by SOC and PT at subject and event level.
- Subject Mappings for TEAEs.
- TEAEs by PT.
- Most Frequent TEAEs by PT.
- Most Frequent Non-Serious TEAEs by PT.
- Relationship of TEAEs to Study Drug by SOC and PT.
- Drug-Related TEAEs by SOC and PT.
- Intensity of TEAEs by SOC and PT.
- Intensity of Drug-Related TEAEs by SOC and PT.
- Pretreatment Events by SOC and PT.

A subject with 2 or more different AEs within the same level of the MedDRA term and TAK-071 dose level and pooled placebo will be counted only once in that level using the most extreme incident for the intensity tables, and related events to study drug for the causality tables.

Most frequent TEAEs are defined as the AEs occurring in at least 2 subjects in any treatment (ie, pooled placebo or individual dose level).

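### Spinal-catheter events may inflate the primary TEAE percentage at the Cohort 3 and Cohort 9 doses relative to pooled placebo, and no planned table separates procedure-related events

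*SAP*

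**What the plan says.** - **Endpoint.** SAP 5.1 lists as primary: "Percentage of subjects who have at least 1 treatment-emergent adverse event (TEAE"). There is no restriction by cause.
- **TEAE definition.** SAP 7.12.1 takes "an AE or a serious AE (SAE) that occurs or gets worse after receiving the first dose of study drug", up to 30 days after the last dose. Procedure-caused events are not excluded.
- **Recording.** Protocol 10.1.3: "PTEs/AEs caused by a study procedure (eg, a bruise after blood draw) should be recorded as a PTE/AE". Protocol 10.2.1.2 also collects, for each event, the investigator's opinion of the "causal relationship to study procedure(s), including the details of the suspected procedure".
- **Who has the procedure.** SAP 4.4.1: "CSF samples for PK analysis will be obtained in Cohort 3 (following a single dose) and Cohort 9 (at steady-state"). Protocol 9.1.15.3: "An indwelling spinal catheter will be inserted into the subarachnoid space". It states no exemption for placebo subjects. It allows CSF sampling in later SRD cohorts if Cohort 3 concentrations are too low. Protocol 6.2.1 describes Cohort 9 as the highest dose of Cohorts 7 to 9.
- **Table layout.** SAP 7.12: "all safety summary tables will be presented by the pooled placebo group, each TAK-071 dose level", plus overall columns, within each part. Protocol 13.1.5 pools placebo across cohorts, separately for SRD and MRD. SAP 7.1.3 defines the non-Japanese MRD cohorts as Cohorts 7 to 12.
- **Causality tables.** SAP 7.12.1 lists 11 summary tables. Those on causality concern study drug only, for example "Relationship of TEAEs to Study Drug by SOC and PT". None uses relationship to study procedure.

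**The concern.** In the two CSF cohorts, dose is confounded with an invasive procedure that almost no comparator subject undergoes. A catheter-caused event with onset after the first dose counts in the primary percentage exactly as a drug effect would. A dose column could then stand above pooled placebo without any drug effect. Because Cohort 9 carries the highest dose of Cohorts 7 to 9, the pattern could look like a dose response.

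The tables by relationship to study drug help only in part. They leave the primary percentage unchanged. Protocol 10.1.6 also lets an event count as related whenever drug involvement cannot be excluded, even if other factors may be responsible, so a catheter event during daily dosing can stay in the drug-related tables.

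These summaries matter beyond this study: under SAP 7.13.1 the interim results of Cohorts 1 to 15 and 17 to 22 support phase 2 planning.

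**Working it through.** **1. Allocation.** The row totals of SAP Table 4.a are 64 + 36 + 16 + 8 + 24 + 18 + 8 + 12 = 186, which matches the stated total. Cohorts 1 to 12, 18 and 19 each have 6 active and 2 placebo subjects. The plan contains no power calculation or event rate to reproduce.

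**2. Catheter exposure, by direct count.**

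| Comparison | Active column | Pooled placebo |
|---|---|---|
| Cohort 3 vs SRD placebo (Cohorts 1-6, 18, 19) | 6/6 | 2/16 (12.5%) |
| Same, with the double-placebo subjects of Cohorts 20-22 pooled | 6/6 | 2/25 (8%) |
| Cohort 9 alone vs non-Japanese MRD placebo (Cohorts 7-12) | 6/6 | 2/12 (16.7%) |
| Cohorts 9 and 12 in one dose column vs the same placebo | 6/12 | 2/12 (16.7%) |
| Cohort 9 vs placebo of Cohorts 7-9 only | 6/6 | 2/6 (33.3%) |

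The fourth row is the likely layout. Columns are set by TAK-071 dose level within the non-Japanese MRD part, and Protocol 6.2.2.2 intends Cohorts 10 to 12 to use the doses of Cohorts 7 to 9.

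**3. Timing.** In Cohort 9 the catheter is used on Day 28, after the first dose on Day 1, so new catheter events fall in the TEAE window. In Cohort 3 there is a predose CSF sample, so events starting at insertion are pretreatment events unless they worsen after dosing. The Cohort 3 figures below count every procedure event and are therefore upper limits.

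**4. Expected difference with no drug effect.** Let b be the background TEAE rate and q the procedure-event rate, independent of each other. Let g and f be the exposed shares of the active column and of pooled placebo.

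- Exposed subject: P(any TEAE) = 1 − (1 − b)(1 − q). Unexposed subject: b.
- Expected difference = (1 − b) × q × (g − f).

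Neither b nor q is in the documents. Assume b = 20-50% and q = 10-70%. Then (1 − b)q runs from 0.5 × 0.1 = 0.05 to 0.8 × 0.7 = 0.56.

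- Cohorts 9 and 12 together, g − f = 1/3: 1.7 to 18.7 points.
- Cohort 9 alone, g − f = 5/6: 4.2 to 46.7 points.
- Cohort 3 vs 16 placebo, g − f = 7/8: at most 4.4 to 49.0 points.

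**5. Chance that the active column shows a higher percentage than pooled placebo.** This is exact binomial enumeration with no drug effect; each range is over b = 20, 30, 40 and 50%.

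| q | Cohorts 9 + 12 (12 vs 12) | Cohort 9 alone (6 vs 12) | Cohort 3 (6 vs 16), upper limit |
|---|---|---|---|
| 0 | 40-42% | 40-43% | 46-49% |
| 10% | 45-46% | 50-53% | 54-61% |
| 30% | 52-59% | 64-75% | 69-82% |
| 50% | 59-70% | 77-89% | 83-94% |
| 70% | 66-81% | 89-97% | 93-99% |

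With placebo from Cohorts 7 to 9 only, Cohort 9 gives 53-88% for q = 30-70%, against 35-39% at q = 0.

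**6. Donepezil in the placebo pool.** Six of the 12 pooled MRD placebo subjects (Cohorts 10 to 12) take donepezil throughout, and their AEs count from Day -21. If Cohort 9 stands alone, this works against the catheter effect. With an assumed extra donepezil event rate of 20-40%, the chance at q = 30% falls from 64-75% to 48-62%. At 40% extra and q = 0 it is 17-29%. If Cohorts 9 and 12 share a column, 6 of 12 subjects on each side take donepezil, and this effect largely balances.

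**7. How much of an excess the procedure would explain.** Add a drug-caused event rate d. For Cohort 3 against 16 placebo subjects at b = 40% and q = 30%, the procedure's share of the expected excess is 100%, 70%, 37% and 18% for d = 0, 10, 30 and 50%.

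**The case against.** A reader might infer that any excess at these doses will be mainly due to the catheter. The documents do not support that. It would be a statement about results and depends on background, procedure and drug event rates that appear nowhere; step 7 shows that it is true under some assumptions and false under others. A reader might also take the Cohort 9-alone figures as the expected case, or conclude that the net bias there must be upward. The first overlooks the likely shared dose column; the second overlooks the donepezil-treated placebo subjects. Nor is the placebo pool free of the procedure, and restriction to Cohorts 3 and 9 is the plan rather than a guarantee.

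The plan already gives partial protection. SOC and preferred-term tables make procedure-type events visible, drug-related TEAEs are tabulated separately, and all AEs are listed. The TEAE tables are descriptive, and no decision rule uses the active-minus-placebo percentage. Cohort 3 is an early SRD step, so an isolated rise there would not resemble a dose response.

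Excluding procedure-attributed events also has a risk. Investigators are blind to treatment but know who has a catheter, so the exclusion falls on the CSF cohorts and could remove true drug events. That rules out making such tables the sole basis for dose statements.

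What remains is the unequal exposure, its entry into an all-cause primary endpoint, and a collected causality field that no table uses.

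**Conclusion.** The point holds as a risk of distortion of unknown size. The catheter may inflate the TEAE percentage at the Cohort 3 and Cohort 9 doses relative to pooled placebo, and the planned tables give no direct way to see by how much. The exposure counts follow from the documents; the percentages rest on assumed rates, independence of event causes and no drug effect. For the MRD part, the shared-column range of 45-81% (40-42% with no procedure events) best matches the SAP layout. The range of 50-97% (40-43% with none) applies only if Cohort 9 stands alone, and donepezil events in the placebo pool would lower it. The Cohort 3 range is an upper limit. A low-cost supplementary analysis is warranted; a change of endpoint is not.

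**What to change.** Keep the primary endpoint and all all-TEAE tables as defined. In SAP 7.12.1:

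1. Add supplementary versions of the TEAE overview and the SOC/PT table that exclude events the investigator assessed as related to a study procedure.
2. Show the CSF cohorts, active subjects and their own placebo subjects, as a labelled subgroup beside the all-TEAE percentages. Include any later SRD cohort to which CSF sampling is extended.
3. State that differences between dose levels and pooled placebo are to be read from both sets of tables together.

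The cost is two or three extra tables from a field already on the AE eCRF. Within a CSF cohort, active and placebo subjects both have the catheter, so the expected procedure-driven difference is zero, but with only 2 placebo subjects that display is descriptive. The downside is the possible loss of true drug events through attribution that is not blind to the catheter, which is why the new tables are supplementary.

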7.12.2 Clinical Laboratory Evaluations

For SRD Cohorts 1 to 6 and 18 to 22, blood samples for clinical laboratory tests (hematology, coagulation, serum chemistry, urinalysis) will be collected at Screening, at Check-in (Day -1), on Days 1 through 5 (Final Visit)/ ET, Day 8, and at the Follow-up Visit. On Day 1, the urine sample for urinalysis will be taken predose (within 2 hours prior to dosing) and the blood sample for these tests will be taken 1 hour postdose. On subsequent days, samples will be taken upon rising in the morning under fasted condition. Laboratory sample collection on Day 8 does not require fasting conditions.

For MRD healthy volunteer Cohorts 7 and 8, blood samples for clinical laboratory tests (hematology, coagulation, serum chemistry, urinalysis) will be collected at Screening, at

Check-in (Day -1), on Days 1, 2, 5, 8, 14, 20, 21, 22, 23 (Final Visit)/ ET and at the Follow-up Visit. On Day 1, the urine sample for urinalysis will be taken predose (within 2 hours prior to dosing) and the blood sample for these tests will be taken 1 hour postdose. On subsequent days, samples will be taken predose upon rising in the morning under fasted condition.

For MRD healthy volunteer Cohort 9, blood samples for clinical laboratory tests (hematology, coagulation, serum chemistry, urinalysis) will be collected at Screening, at Check-in (Day -1), on Days 1, 2, 3, 8, 9, 10, 15, 20, 27, 28, 29, 30 (Final Visit)/ ET and at the Follow-up Visit. On Day 1, the urine sample for urinalysis will be taken predose (within 2 hours prior to dosing) and the blood sample for these tests will be taken 1 hour postdose. On subsequent days, samples will be taken predose upon rising in the morning under fasted condition.

For MRD + Donepezil pretreatment healthy volunteer Cohorts 10 to 12, blood samples for clinical laboratory tests (hematology, coagulation, serum chemistry, urinalysis) will be collected at Screening, at Check-in (Day -22), on Days -21, -10, -1, 1, 2, 5, 8, 11, 14, 20, 21, 23 (Final Visit)/ ET and at the Follow-up Visit. On Day 1, the urine sample for urinalysis will be taken predose (within 2 hours prior to dosing) and the blood sample for these tests will be taken 1 hour postdose. On subsequent days, samples will be taken predose upon rising in the morning under fasted condition.

For MRD Japanese healthy volunteer Cohorts 13 to 15, blood samples for clinical laboratory tests (hematology, coagulation, serum chemistry, urinalysis) will be collected at Screening, at Check-in (Day -1), on Days 1, 2, 3, 8, 9, 10, 15, 20, 27, 28, 29, 30 (Final Visit)/ ET and at the Follow-up Visit. On Day 1, the urine sample for urinalysis will be taken predose (within 2 hours prior to dosing) and the blood sample for these tests will be taken 1 hour postdose. On subsequent days, samples will be taken predose upon rising in the morning under fasted condition.

For Cohort 16 in subjects with MCI or Mild AD, blood samples for clinical laboratory tests (hematology, coagulation, serum chemistry, urinalysis) will be collected at Screening, at Run-in Period (Day -21), at Check-in (Day -1), on Days 1, 2, 11, 20, 21, 22, 41, 42, 43, 52, 61, 62, 63 (Final Visit)/ ET and at the Follow-up Visit. On Days 1 and 41, the urine sample for urinalysis will be taken predose (within 2 hours prior to dosing) and the blood sample for these tests will be taken 1 hour postdose. On all other days, samples will be taken predose upon rising in the morning under fasted condition.

For BA/FE Cohort 17, blood samples for clinical laboratory tests (hematology, coagulation, serum chemistry, urinalysis) will be collected at Screening and in each period at Check-in (Day -1), 30 minutes postdose on Day 1, upon rising on Days 2 and 5 and, at PK visit on Day 8 (Day 8 of Period 3 is the final visit), at ET, if occurs, and Follow-up Visit (Day 12 [±2]) of Period 3, as appropriate.

Descriptive statistics (N, mean, median, SD, minimum and maximum) of clinical safety laboratory variables will be summarized by the pooled placebo group, each TAK-071 dose level, TAK-071 overall, and overall total within each part (SRD cohorts, MRD cohorts, Cohort 16, and Cohort 17) for baseline, each postdose time point, and change from period baseline to postdose

time points in International System of Units (SI). Only the scheduled measurements will be included in the summary. No statistical tests will be performed.

Individual results for hematology, chemistry, and coagulation laboratory tests will be evaluated against the Takeda predefined laboratory MAV criteria ([Appendix A](#)) using the result and criteria in SI units. All subjects with results that meet the MAV criteria will be presented in a data listing. The number and percentage of subjects with at least one postdose markedly abnormal laboratory test result will be summarized. The mapping of the subjects who meet the MAV criteria for postdose lab results will be listed as a table. All postdose clinical lab results, including scheduled and unscheduled measurements will be included in the MAV summaries.

All clinical laboratory data will be presented in both SI and conventional units in data listings.

